## **12.2** Statistical analysis plan

#### Primary analysis

There will be three categories for the level of agreement: complete agreement, clinically unimportant difference and clinically important difference. For each sample, three sets of agreements will be reported:

- whether each pathologist's DP and LM diagnoses concur
- whether each of the four DP diagnoses concur with the GT
- whether each of the four LM diagnoses concur with the GT

Two measures will be used to quantify concordance: percentage concordance and ICC. Logistic regression models will be used to estimate the probability that diagnoses are concordant and will include a random effects term to account for multiple results per sample.

For cancer resections, as well as diagnosis, comparisons will also be made across all RCPath dataset items.

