## 7.4 Reporting pathologists

Six NHS histopathology laboratories (Coventry, Belfast, Lincoln, Oxford, Nottingham, Birmingham) will each have specialist pathologists to report on relevant disease areas. In each area, four pathologists will report the same series of samples twice, once each with LM and DP, thereby allowing comparison within and between observers over both platforms.

Centre/disease specialty	GI	Skin	Breast	Renal
Coventry	[name]	[name] [name]		[name]
Belfast	[name] [name]	[name]	[name]	
Lincoln		[name]	[name]	
Nottingham	[name]		[name] [name]	
Oxford				[name] [name]
Birmingham				[name]

Specialist reporting pathologists at each centre by specialty are shown below:
--

The estimated time to make these readings based on current work-diary exercise data is one 4 hour session per week over 24 months.

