## **12. STATISTICAL ANALYSIS**

## **12.1** Power and sample size

Three measures will be used to quantify concordance in this study: percentage concordance, Kappa Statistic (KS) and intra class correlation (ICC). In consideration of the appropriate sample size for this study, we assessed the precision of percentage concordance estimates.

Percentage concordance for the routine samples is assumed to be 98.8% (7). The percentage concordance for the difficult samples ranges from 40%-70% (16-25), and so we assume it to be 55%. We assume the percentage concordance for moderate samples to be 75% (a percentage between those for difficult and routine samples). The weighted percentage concordance within our study, with the specified 10% difficult, 10% moderate and 80% routine proportions, is expected to be 90%.

For each of breast, GI and skin, 600 specimens will be included, leading to 4,800 diagnoses (i.e. 600\*4 pathologists\*2 readings). For renal, 200 specimens will be included, leading to 1,600 diagnoses.

Taking into account the expected percentage concordance, we take ICC for routine, moderate and difficult samples to be 0.9, 0.7 and 0.4 respectively. This corresponds to an overall ICC of about 0.8. Hence, the design effect is (1+ICC(observations per specimen-1))=3.4.

Consequently, 2400 paired diagnoses (a pair consists of DP and LM diagnoses of each sample by a pathologist) is equivalent to 705 (2400/3.4) independent observations. With 705 independent observations the margin of error (1.96 x Standard error) is 2.2% so that the precision while analysing breast cancer, skin and GI specimens separately is high. Due to a smaller sample size for renal specimens, the margin of error is 3.1%.

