In addition to these publications, UHCW, the lead trust and sponsor, plans a series of press releases and media interviews on the progress and findings of the studies. We plan reports to the NHS Patient Safety Group regarding the costs of pathology errors, the role of DP in reducing error through improved expert and peer review of samples, and findings of the eye tracking study.

Generalisability of findings across pathologists with different levels of expertise:

The study pathologists are all NHS consultants and range in experience from 3 to 35 years consultant experience, working in a mix of teaching hospital and district general hospital pathology departments across the UK. The study will recruit a trainee pathologist as its Research Fellow. Three pathologists are already using digital pathology for routine practice.

We will develop a strategy in consultation with our PPI group and UHCW/Warwick University Communications team (e.g. a lay summary of the findings available on the study websites, and dissemination through social media) to help patients, patient representatives and wider public learn about the project's findings.

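### The primary model and the 2.2% margin allow for clustering by sample but not by pathologist, so the intervals hold for the study readers and are too narrow, by an unknown amount, for pathologists in general

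*Protocol*

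**What the plan says.** Section 7.4 sets a fully crossed design within each specialty: "In each area, four pathologists will report the same series of samples twice, once each with LM and DP". Each reader therefore supplies 600 DP/LM pairs in breast, GI and skin, and 200 in renal.

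Section 12.1 starts from 600 specimens per large specialty ("600 specimens will be included, leading to 4,800 diagnoses"), which is 2,400 pairs. It takes an expected concordance of 90% and a within-specimen ICC of 0.8 ("This corresponds to an overall ICC of about 0.8"). It then inflates the variance for specimen alone: "Hence, the design effect is (1+ICC(observations per specimen-1))=3.4". This leads to 705 effective observations and margins of error of 2.2% for breast, GI and skin, and 3.1% for renal.

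Section 12.2 (Primary analysis) specifies logistic regression models that "include a random effects term to account for multiple results per sample". No pathologist term, fixed or random, is named. Under Subgroup analyses, the main analysis pools all specialties, and each specialty alone is a subgroup.

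Two other places bear on this. Section 6 lists individual pathologists' non-concordance rates as a secondary outcome. Section 15 names a multiple-reader, multiple-sample design, but only for eye tracking.

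**The concern.** The primary outcome is agreement between a pathologist's own DP and LM diagnoses, so it depends on the reader as well as on the slide. The protocol gives reason to expect readers to differ. Section 3 describes a mix of senior, junior and early-adopter pathologists, most of them new to DP. Section 19.2 gives a range of 3 to 35 years of consultant experience, with three readers already using DP routinely.

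If readers differ, the mean of four readers carries a variance component that more specimens cannot reduce. Neither the named random effect nor the design effect contains it. An interval built this way answers how well these four readers agree with themselves on slides of this kind. Section 2 frames the study around adoption of DP across the NHS, and section 12.1 calls the specialty precision high. A reader is therefore likely to take the interval as applying to other pathologists too.

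**Working it through.** **Inputs from section 12.1:** concordance p = 0.90; ICC = 0.8; 4 pairs per specimen; 2,400 pairs per large specialty; multiplier 1.96. **Input from section 7.4:** 4 readers per specialty, hence 16 reader places. **Assumed, because the protocol gives no value:** s, the between-reader SD of true concordance, from 0.5 to 3 percentage points.

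**1. The plan's own figure.** Design effect = 1 + 0.8 × (4 − 1) = 3.4. Effective n = 2,400/3.4 = 705.9, which the plan gives as 705. Margin = 1.96 × √(0.90 × 0.10/705) = 2.21%. The stated 2.2% reproduces, with clustering by specimen only.

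**2. Adding readers, one specialty.** Variance = p(1 − p)/705 + s²/4. In squared percentage points the first term is 1.277. Coverage of the planned interval, for pathologists in general, is P(|Z| < 1.96 × √(1.277/total variance)).

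| Assumed s (points) | s²/4 | Total variance | Margin | Coverage of planned interval |
|---|---|---|---|---|
| 0 | 0 | 1.277 | 2.2% | 95% |
| 0.5 | 0.0625 | 1.339 | 2.3% | 94.4% |
| 1 | 0.25 | 1.527 | 2.4% | 92.7% |
| 2 | 1.00 | 2.277 | 3.0% | 85.8% |
| 3 | 2.25 | 3.527 | 3.7% | 76.2% |

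The reader part alone is 1.96 × s/2, which is 1.96 points at s = 2 however many specimens are read.

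**3. Adding readers, all specialties.** Pairs = 2,000 × 4 = 8,000. With the same ICC and 90% concordance throughout, effective n = 8,000/3.4 = 2,353. The sample-only variance is 0.3825 and the margin 1.2%. With 16 reader places weighted equally, s²/16 is added.

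| Assumed s (points) | s²/16 | Total variance | Margin | Coverage of planned interval |
|---|---|---|---|---|
| 0 | 0 | 0.3825 | 1.2% | 95% |
| 0.5 | 0.0156 | 0.398 | 1.2% | 94.5% |
| 1 | 0.0625 | 0.445 | 1.3% | 93.1% |
| 2 | 0.25 | 0.6325 | 1.6% | 87.3% |
| 3 | 0.5625 | 0.945 | 1.9% | 78.8% |

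Equal weighting is slightly favourable. Weighted by pairs, 12 places carry 600/8,000 each and 4 carry 200/8,000 each. The multiplier is then 12 × 0.075² + 4 × 0.025² = 0.070 instead of 0.0625, and the margin at s = 3 is 1.96 × √(0.3825 + 0.63) = 2.0%.

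**4. Renal.** The stated 3.1% reproduces as 3.08% with ICC 0.4 and 90% concordance: 800/2.2 = 363.6 effective observations. It too has no reader term. Adding s²/4 gives 3.2%, 3.7% and 4.3% at s = 1, 2 and 3.

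**The case against.** Five arguments can be made on the other side.

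- **Size.** The protocol gives no reader SD, and at 0.5 or 1 point the planned intervals still cover about 93% to 94.5%. A reader might infer that coverage is well below 95% whatever the SD. The documents do not support that; it follows only if readers differ by about 2 points or more. This argument stands.

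- **Target.** The primary objective compares the same pathologists' own diagnoses, and section 12.1 sets a precision, with no margin or decision rule that a wider interval would overturn. The line in section 19.2, "Generalisability of findings across pathologists with different levels of expertise", introduces a description of the readers' experience and makes no inferential claim. For the study readers a sample-only model is acceptable. This stands in part: the purpose is NHS adoption, and the protocol nowhere limits its intervals to these readers.

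- **Silence is not exclusion.** Section 12.2 does not say that the sample effect is the only term, and a SAP could add others. That is fair for the model, but it does not help section 12.1, where the sample-only calculation is complete.

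- **Slack in the planning figure.** An ICC of 0.8 may be conservative. The difficulty mix alone ("10% difficult, 10% moderate and 80% routine proportions, is expected to be 90" per cent, though the weights compute to 92.04%) implies an ICC of [0.8(0.988 − 0.9204)² + 0.1(0.75 − 0.9204)² + 0.1(0.55 − 0.9204)²]/(0.9204 × 0.0796) = 0.28. At 90% concordance the sample-only margin would then be 1.6%, and 2.2% would be passed only when s exceeds about 1.5 points. This protects the planning figure; it does not protect intervals from a fitted model that lacks a reader term.

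- **Reader differences will be visible.** Individual non-concordance rates are already a secondary outcome. That is true and useful, but those rates do not enter the primary interval.

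A reader might also infer that leaving the randomised reading order out of the model is a further error. Order is randomised by batch with two readers in each order, and the outcome is agreement within a pair. Nothing in the protocol shows a bias or a wrong interval from its absence.

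**Conclusion.** The omission is in the protocol's text: both the named random effect and the design effect cover clustering by sample only, in a design where the same four pathologists read every sample of a specialty. The intervals are sound as statements about the study readers and too narrow for pathologists in general. Over assumed reader SDs of 0.5 to 3 points, the specialty margin is 2.3% to 3.7% against the stated 2.2%, and the all-specialty margin is 1.2% to 1.9% against 1.2%.

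These sizes rest on the assumed SD, on the plan's 90% and ICC of 0.8, on a normal approximation and, for the pooled figures, on the same inputs for renal and on 16 separate readers. Names are removed from the table in section 7.4, so up to 16 reader places is the most that can be said.

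This is worth settling before analysis. It is not a fatal flaw, because in the specialty analyses much of the remedy is a clear statement of scope.

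**What to change.** **Section 12.2, all-specialty analysis.** Fit crossed random effects for sample and pathologist (up to 16 reader places).

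**Section 12.2, specialty analyses.** Four readers estimate a variance poorly: with 3 degrees of freedom the t multiplier is 3.18 against 1.96. Show each reader's concordance beside the estimate, using the secondary outcome already planned, and state that the interval is conditional on those four readers. A fixed pathologist effect would not widen the interval, so it does not replace that statement. If inference to other pathologists is wanted within a specialty, use a method that treats both samples and readers as random, such as a sample-by-reader bootstrap, and accept that four readers limit it.

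**Section 12.1.** State that 2.2% and 3.1% are conditional on the readers, and add the sensitivity range over reader SD.

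**Cost.** Changes of wording and model specification only. The analysis needs only which pathologist made each report, and reports are already assigned and completed by pathologist on the study database. The intervals meant for general use become somewhat wider.

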#### Interim analysis

Interim reports will be created after approximately 6 and 12 months from the start of sample enrolment into the main study informing on the selection of samples and the flow and timing of pathology reviews. The steering group, who will advise if any adjustments are required, will review these data. If it is concluded that the enrolment of suitable samples is falling well below target or substantial delays in pathology review are making the required sample flow rates unattainable, and that suitable protocol amendments cannot be determined to rectify the situation, then this may require alterations of milestones which will be agreed by the steering group to ensure successful delivery of this study.

#### Subgroup analyses

The above analyses will be performed using specimens from all specialties. Subgroup analyses will investigate results from each of the four specialties separately. The subgroups containing routine, moderate and difficult samples will also be explored.

#### Procedure(s) to account for missing or spurious data

We will utilise a bespoke tracking database designed for this study, which will record and update the progress of the study. It will auto-populate updates to show the sample enrolment rates, track the inventory (glass slides) and notify pathologists to submit the reports. Additionally, a Research Fellow will be employed in the study to rigorously oversee the flow of study samples. They will ensure safe and timely transition of samples between pathologists. Thus, we anticipate little to no missing data.

## **13. HEALTH ECONOMICS EVALUATION**

#### Aim

The aim of the health economic study will be to assess the incremental costs involved in DP vs LMbased pathology and estimate the health benefits and resource use impact of a sample of diagnostic inaccuracies identified in the study, in order to support an informed assessment of the sample for investing in DP-based pathology processes.

#### Methods and analysis

This aim will be achieved by answering the following questions, which have been identified in consultation with our PPI colleagues:

- 1. What are the costs involved in investing in DP?
- 2. What is the knock-on effect on resource use within pathology of switching to DP, resulting from the process efficiencies it enables?
- 3. Where does the switch from LM to DP generate value for patients and the health service, as a consequence of improved speed and accuracy of the provision of diagnostic information?
- 4. What health benefits and cost impacts accrue as a result?

Data from existing deployments of DP in the study group will inform the estimates of cost to implement DP. A micro-costing exercise will then be carried out to assess the impact of DP on process efficiency. This will involve direct observation of existing LM reporting and multi-disciplinary team (MDT) processes including time for supervising histopathology trainees.

During the study, DP reporting and MDT processes will be observed to inform a comparative costing exercise. Costings derived from the timing and staff grade required for each task in the process will be performed, allowing direct comparison of the two different workflows. Pathologists will be required to assess the time taken to report samples on DP compared to LM by stopwatch. Making corrections for interruptions, pathologists will record the time taken to examine slides and compile the reports on all samples in the study both on DP and LM.

How these measurements change over the time of the study will be assessed so allowances can be made for increasing experience with DP. The cost of peer review of samples between pathologists using DP compared to LM will also be estimated. This will include peer review of samples within departments, and referral for expert review outside of the department. The cost of collation of samples for MDT review will also be compared between DP and LM. This will include stopwatch recording of the time taken to find sample slides for the MDT review, as well as the time taken to review slides for MDT with DP and LM workflows.

This detailed information will be used to estimate throughput and capacity under each system. The simulation model for UHCW breast cancer pathway developed by Madan et al. will be used to estimate how increased throughput might lead to reductions in delays along the diagnostic pathway (up to the point at which the treatment plan has been finalised). A similar model will be developed for the other cancers in the study (GI, skin and renal).

Drawing on expert guidance, illustrative examples of the potential gains from increased throughput and the resulting reduction in time to treatment initiation will be presented. Any differences in diagnostic accuracy will lead to potential changes in health outcomes and the cost of health care provided. Potentially, there may be a range of choices around treatment which might be influenced by diagnostic accuracy, and it is unlikely to be feasible to assess such changes for every example found in the study. Therefore, we will focus on examples where the impact is likely to be significant. This follows previous work done at Warwick Medical School which identified HER2 status as information where changes in diagnostic accuracy could lead to substantial impact on health outcomes and treatment costs. We will identify similar examples from incremental improvements in diagnostic efficiency identified in the study, and determine the likely number of similar samples that might be processed in the service per annum. We will identify suitable cost-effective cancer treatment models from the existing literature to source estimates of the health and cost impact of correct versus incorrect diagnosis. This work will allow us to provide only a partial estimate of the downstream costs and benefits of investing in DP, as it will not cover all the samples where it might impact treatment. However, we will be able to assess whether the samples identified are sufficient to justify investment in DP. If not, we will provide estimates of the further benefits required beyond those identified within the study, together with an expert-based assessment of the plausibility of observing these additional benefits in practice.

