This study is designed around teams of four pathologists, blind to the original diagnoses, all examining the same series of samples, using both LM and DP. The modality each pathologist views/reports on first will be randomised for each batch of samples, and there will be a minimum of a six-week washout period between LM and DP viewings. Reports will then be scrutinised by a trained Research Fellow independent of the reporting pathologists. Differences detected will be classified by an independent pathologist into clinically important (would alter the clinical management) or clinically unimportant (would not alter the clinical management). The original diagnosis will serve as the reference diagnosis. The ground truth (GT) for each sample is decided on conclusion of the readings, by consensus of the study pathologists, taking into account the reference diagnosis. This allows comparison of each pathologist's performance on LM and DP against the GT. The study will examine 2000 histopathology samples including 600 samples each of breast, gastrointestinal (including 200 cancer screening samples) and skin, and 200 renal samples taken for native or transplant related renal disease. The renal biopsies will include immunofluorescence for detection of immunoglobulin deposits. The population of samples enrolled will be a combination of sequentially selected samples and those from study centres' archives. With the exception of renal, samples will also be enriched with at least 10% moderately difficult and at least 10% difficult samples.

A Health Economic evaluation will involve estimating the core costs and benefits associated with DP, compared with LM. This will involve estimating the impact of switching to DP on throughput, and translating this into the impact on the time to establishing a treatment plan. It will further involve assessing samples of discrepancy to investigate the impact on treatment decisions, and the incremental costs and benefits resulting from this impact. This will be for all discrepancies if feasible, or a purposive sample (selected based on material impact on health and cost outcomes).

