## 7. SAMPLE PATHWAY

## 7.1 Sample selection criteria

Histopathology samples from five participating NHS trusts will be selected. All samples are collected for the purpose of routine histopathology reporting and only entered into the study on completion of their clinical review at the respective NHS participating site.

There are four sub-specialty areas that are included in the study: breast, gastrointestinal (GI), skin and renal. The sample selection process will be devised to include cancer screening biopsies and will be enriched (20%) for areas of difficulty, with the exception of renal samples where all are considered difficult cases:

- Breast (Belfast, Coventry, Lincoln & Nottingham): A total of 600 samples including at least 200 cancer screening biopsies enriched with:
  - o At least 10% resected tumours (moderately difficult)
  - 10% difficult samples: low grade ductal carcinoma in situ, atypical hyperplasia, screening category B3 and B4, lesions with calcium oxalate (Weddellite calcification), sclerosing and papillary lesions, and micrometastases
- GI (Coventry, Belfast & Nottingham): A total of 600 samples including at least 200 cancer screening biopsies enriched with:
  - At least 10% resected tumours (moderately difficult)
  - 10% difficult: oesophageal dysplasia, polyp cancers, inflammatory bowel disease, minimal change colitis, graft versus host disease, giardiasis, cytomegalovirus, H. pylori and herpes virus infection
- Skin (Coventry, Belfast & Lincoln): A total of 600 samples enriched with:
  - o At least 10% non-basal cell carcinoma cancer resections (moderately difficult)
  - 10% difficult: sentinel nodes, dysplastic naevi, spitz naevi, lentigo maligna, early and desmoplastic melanoma, herpes virus infection, leischmaniasis, leprosy, amyloid, angioscaroma, and Kaposis sarcoma
- Renal (Oxford only): A total of 200 sequential native biopsies for glomerular, tubulointerstitial and vascular disease and transplant biopsies for graft rejection. No enrichment is planned in the renal biopsy group as all of these biopsies are difficult to report.

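### Section 13 draws its worked economic examples from improvements, against the direction-neutral rule in section 2, and plans a renal cancer pathway model although no renal cancers are sampled

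*Protocol*

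**What the plan says.** **How examples are chosen.** Section 2 describes the assessment of discrepancies for their effect on treatment decisions, costs and benefits: "This will be for all discrepancies if feasible, or a purposive sample (selected based on material impact on health and cost outcomes". The Aim in section 13 is to "estimate the health benefits and resource use impact of a sample of diagnostic inaccuracies identified in the study". Methods and analysis in section 13 says that not every example can feasibly be assessed and continues: "Therefore, we will focus on examples where the impact is likely to be significant". After citing HER2 status as a model case, it states where further examples come from: "We will identify similar examples from incremental improvements in diagnostic efficiency identified in the study". The number of similar samples handled per year in the service is then estimated.

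**What the examples are used for.** The protocol concedes that the downstream estimate is partial, but adds that "we will be able to assess whether the samples identified are sufficient to justify investment in DP". If they are not sufficient, it will estimate what additional benefit would be needed and ask experts how plausible that is.

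**Renal.** The breast cancer pathway model is to be extended: "A similar model will be developed for the other cancers in the study (GI, skin and renal". Section 7.1 defines the 200 renal samples as "native biopsies for glomerular, tubulointerstitial and vascular disease and transplant biopsies for graft rejection".

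**The concern.** An investment judgement needs both sides of the diagnostic ledger: cases where DP corrects an LM error, and cases where DP introduces one. If the examples that are costed, scaled up and weighed against the price of DP come only from improvements, the benefit side is overstated. Scaling to annual volume multiplies the overstatement.

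Unfavourable cases are foreseeable on the protocol's own account. Section 2 notes that most DP systems resolve less finely than LM, and section 3 notes that some studies question the suitability of DP for diagnosis.

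The renal wording is a separate matter. A cancer pathway model, with treatment consequences taken from published cancer models, does not describe biopsies taken for native kidney disease or graft rejection. It would say nothing about the renal samples that the study actually reads.

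**Working it through.** The protocol states no figure for the economic evaluation, so there is none to reproduce. The check is a comparison of passages, followed by an illustration.

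**1. Selection rule, place by place.**
- Section 2: all discrepancies, or a purposive sample by material impact. Neutral.
- Section 13, Aim: a sample of inaccuracies. Neutral.
- Section 13, Methods, the sentences leading up to the HER2 example: any difference in accuracy, with a focus on large impact. Neutral.
- Section 13, Methods, the sentence saying where the examples come from: improvements. One direction.
- Section 13, Methods, fallback if the examples do not suffice: further benefits only. One direction.
- Section 13, question 3: presupposes better speed and accuracy. One direction.
- Section 6: one secondary outcome covers non-concordance and the cost of error (neutral); the next speaks of DP reducing error (one direction).

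Section 13 itself regards assessing every example as unlikely to be feasible, so the purposive branch of the section 2 rule is the one likely to apply. For that branch, section 13 names improvements as the source, and no matching sentence draws cases where DP is worse. The two rules do not agree.

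**2. Are the data for both directions available?** Yes. Section 12.2 compares each reader's DP diagnosis and LM diagnosis with the ground truth (GT). The legend to Figure 3 has the readers agree a GT wherever there is a clinically important difference. Direction can therefore be read off for exactly the cases that matter.

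**3. Illustration of the effect.** Inputs from section 12.1: 2,400 pairs in each of breast, GI and skin, and an expected concordance of 90%. Assumption, not in the protocol: a share *f* of discordant pairs in which DP is right, with LM right in the rest.
- Discordant pairs: 3 × 2,400 × (1 − 0.90) = 720.
- Improvements-only count: 720 × *f*. Net count: 720 × (2*f* − 1).

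| *f* (assumed) | Improvements only | Net of both directions |
|---|---|---|
| 0.3 | 216 | −288 |
| 0.5 | 360 | 0 |
| 0.7 | 504 | +288 |

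The weights in section 12.1 actually give 0.8 × 98.8% + 0.1 × 75% + 0.1 × 55% = 92.04%. That leaves 7,200 × 0.0796 = 573 discordant pairs. The improvements-only counts become 172, 287 and 401, against nets of −229, 0 and +229. The pattern is the same: the one-sided count stays positive whatever the true balance.

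These are head-counts of pairs of any clinical importance, not costs or health effects.

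**4. Renal.** Section 13 lists renal among the cancers. Sections 2 and 7.1 allow only native kidney disease and transplant biopsies, and name no tumour category. Section 13 also has reporting times recorded for every sample on both platforms. Renal DP and LM times will therefore exist, but for non-cancer biopsies.

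**The case against.** The best defence is that one word is being made to carry too much. A reader might infer that the protocol counts improvements only and excludes cases where DP is wrong. It does not say so: section 2, the Aim in section 13 and the sentences leading up to the disputed one are neutral, and the text after it speaks of correct versus incorrect diagnosis and of costs as well as benefits. The disputed phrase also concerns diagnostic efficiency, which is not plainly accuracy. This stands, and it limits the point to a conflict between two rules. It does not remove the conflict, because the one-directional sentence is the one that says where the examples come from.

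A reader might also infer that a positive net benefit is built in. It is not: the cost of DP enters the judgement, and the protocol provides for the examples proving insufficient. What may be overstated is the diagnostic gain, not necessarily the final balance. The admission that the estimate is partial concerns coverage and does not address direction.

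The illustration is open to fair criticism. It rests on an assumed *f*, takes one reading in each discordant pair to be right when both may differ from the GT, and tallies all pairs although the protocol plans selected examples.

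On renal, the word for cancers may be loose shorthand for the specialties. A reader might go further and say that the renal model would have no study data; that is too strong, given the reporting times. What remains is that no data on renal cancer diagnosis or its pathway will come from this study.

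**Conclusion.** The point holds as two inconsistencies within the protocol. First, section 13 takes its scaled-up examples from improvements, while section 2 admits discrepancies in either direction. Followed literally, section 13 would credit DP with its gains and leave out offsetting errors before drawing the investment conclusion. This is a risk that depends on which text is followed, not an established bias. Secondly, a renal cancer pathway model is planned for a renal sample that contains native and transplant biopsies only.

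The size of any tilt cannot be computed from the protocol, which gives neither the split of discordances by direction nor their costs. The counts above show only how a one-sided tally behaves over an assumed *f* of 0.3 to 0.7. The secondary economic evaluation is affected; the primary intra-pathologist concordance analysis is not.

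**What to change.** **Selection.** Reword section 13 so that clinically important differences against the GT are eligible in either direction (DP right and LM wrong, or the reverse) under the same material-impact criterion as section 2. Scale both kinds to annual volume in the same way, and report the net effect before the investment conclusion. The fallback should start from that net effect.

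Assessing every difference, or a random sample stratified by direction, would be stronger on bias. Given the feasibility limit that section 13 states, and the chance that a random draw misses rare high-impact cases, that is a trade-off for the team and not a requirement.

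**Renal.** Limit the additional cancer pathway models to GI and skin, beside the existing breast model. For renal, either model the native and transplant biopsy pathway, or confine the analysis to the reporting-time and cost data already planned.

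**Cost.** Changes of wording and no new reads, since the comparisons with the GT are already planned. There is some extra modelling for the unfavourable examples, and more if a renal biopsy pathway is built. The net benefit may turn out less favourable to DP.
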